1.4.2 Secondary outcomes

- Distribution of policies across a scale of potential to achieve system change (Potential of policies)
- Perceptions of:
 - Personal and shared local understanding of DHI (Understanding)
 - Personal and shared commitment to address DHI locally (Commitment)
 - Strength of local collaborations to address DHI (Collaboration)
 - Confidence that additional solutions to address DHI locally will be implemented in the next 12 months (Confidence)

2 Methods

This protocol presents the quantitative data collection methodology led by the University of Cambridge, followed by the qualitative process evaluation methodology led by the University of Hertfordshire (Section 2.8)

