1.2 The Intervention

The intervention was co-developed by MW, KP and AS with Jersey’s public health team, then refined and delivered in Guernsey. The Association of Directors of Public Health confirm DHI are a high priority, and the intervention would be attractive.

The intervention will be flexible to local context, is described using the Template for Intervention Description and Replication, (11) is supported by a Theory of Change (**Figure 1**), will be delivered by the research team and comprise:

- 1 or more online 2-hour pre-meet with the key informant (defined below; and relevant team members) ~3 months pre-workshop to review roles, agree upon a focus, and identify workshop participants. Workshop participants (n~15) will be local decision makers in any sector with the power to enact workshop insights (12) and representatives of local community food organisations to bring the voice of those with experience of DHI. Conducting GMB in one day is ambitious but necessary to maintain engagement. Focusing on one locally-agreed population or outcome (e.g.

children, vegetable intake) makes one-day manageable and the intervention flexible to local context. Follow-up meetings will be conducted as required.

- intelligence website circulated to workshop participants summarising local data on DHI to provide context. To be developed by Food Foundation from routinely available data (<https://fingertips.phe.org.uk/>) and their regular food security surveys. Including e.g. local prevalence of children in poverty not eligible for free school meals, type 2 diabetes and food insecurity.
- one-day in-person GMB workshop, developing a CLD and using this to identify potential solutions. Guided by manuals and scripts. Facilitated by 2-3 researchers.
- Around three online 1-2 hour post-meets with key informants (and team) 1 week, 1 month and 3 months post-workshop to refine the CLD, identify further solutions, and support solution prioritisation. Informed by our comprehensive database of Food System Transformation Solutions enabling sharing of best practice.(13)

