2.1 Trial Design

A single-centre, unblinded, parallel-group, superiority randomised controlled trial with 1:1 allocation, alongside a mixed-methods process evaluation.

LAs that are randomised to the control arm of the trial will be provided with intervention materials at the end of the study.

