2.5 Randomised Control Trial Data collection

2.5.1 Local authority level baseline and 12-month data collection for primary outcome

Based on the logic model described in Figure 2, data will be collected from each LA on the primary outcome at baseline and 12 months to document existing policies related to dietary inequalities prior to randomisation and intervention implementation. These data provide a reference point for assessing change at the 12-month follow-up interview. A structured interview guide will be used with a checklist of questions (**Table 1**) to identify policies. All interviews will be recorded on Microsoft Teams. Interviews will be conducted by a member of the research team with the LAKI. The interview recording and generated transcription will be stored until the data capture form has been completed and will then be deleted.

Table 1. Key Informant interview guide for baseline data collection

| Variable | Interview guide |
|----------------------------------|--|
| Date | 1. Date of data collection |
| LA and KI information | 
 1. Name of LA 2. What role does the Key Informant have 3. How long as the Key informant been in their current role? 4. How long has the Key Informant been in a role relevant to dietary inequalities |
| Current food strategies | 
 1. Does the LA have a current Food Strategy (Y/N) 2. Is the LA part of a local food partnership (Y/N) 3. Is the LA a member of the Health Determinants Research Collaboration (Y/N) |
| Current policies for DHI (known) | 1. Can you tell me what policies have been put in place in the last 12 months or will be put in place in the next 12 months to address dietary inequalities (defined as any intentional actions explicitly aiming to address dietary inequalities)? Use relevant prompts with examples from the Food System Transformation Solution Bank |

| | |
|--|---|
| | 
 2. For each policy: what was (or will be) the date of implementation? 3. For each policy: please tell me more about that, what it involves etc Is there anything else that's relevant for this policy? (for each response on a particular policy, ask again about details and repeat until data saturation is achieved for that policy). 4. Are there any other policies in place to address dietary inequalities? Repeat the above questions (i.e., 2-4) for each policy until all policies known to the Key Informant are given. |
|--|---|

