3.2 Randomisation & Enrolment

Trial LAs will be unblinded (open label) and randomised using a computer-generated randomization list with a 1:1 ratio. Specifically, our study statistician will generate the randomisation list using Stata statistical software. Stata makes use of a computer system clock as the seed point, which produces a pseudo-random list generally regarded as acceptable for RCTs.

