3.3 Analysis Plan

The main analysis will use linear regression to compare the mean number of policies between intervention and control groups, adjusted for baseline. It will include all LAs in the group they were randomized to (i.e., intention-to-treat). We will similarly assess changes in potential of policies to achieve system change, and Understanding, Commitment, Collaboration and Confidence in an RCT framework in LA key informants at baseline and 12 months; and in a pre-post framework in all workshop participants at the start and end of workshops. Exploratory interaction and sub-group analyses will assess if the intervention is differentially effective in LAs based on differentiating characteristics between LAs (for example those in HDRC partnerships or those with food strategies) to gain insight to DHI-focused policy implementation and understand better any potential limitations to generalizability.

Qualitative data will be managed and thematically analysed (Thorne S 2000) using NVivo, following an iterative, interpretive coding process:

- Open coding (informed by Theory of Change (**Figure 1**)): initial identification of key ideas, actions, participant responses, mechanisms, and contextual influences emerging from the data.
- Axial coding: Organisation and refinement of codes into broader analytic categories e.g. implementation fidelity, mechanisms of change, contextual influences, and the evolution of understandings and practices over time.
- Integrative analysis (selective coding): development of an integrated explanatory account, informed by realist principles, which explores how mechanisms operate under different contextual conditions and how this varies between GMB and control settings.

Analytic credibility will be supported through triangulation across observations, interviews, and documentary sources, and through comparative analysis of GMB and control settings with attention to contextual variation and emergent processes. Where appropriate, qualitative findings will be used to aid interpretation of quantitative outcome measures. In order to provide context for the data collection and analysis we will scope relevant documents including:

- workshop agendas, scripts, attendance lists, CLDs and other workshop outputs

- LA food strategy documents, policy submissions
- Food Foundation DHI data

4 Data Management

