4.1 Data storage

Data will be handled and stored in line with IMS Epidemiology data management policies for all quantitative data collected.

For interviews recorded on Microsoft Teams, the data will initially be captured as a video/audio mp.4 file. This recording will automatically save into OneDrive on the University's Microsoft's 365 platform which the study researcher has access to using their RAVEN credentials. The Microsoft Teams functionality for transcription will also be used during the interview. Following the interview, a transcript will be available in Teams and will be downloaded into OneDrive as a Word document. Following the interview, the video/audio mp.4 file will be converted to an audio only mp.3 file, using the software VLC. The audio only mp.3 file and transcript Word document, will then be saved into the IMS Epidemiology Unit's Secure Research Drive (SRD), a separate server which requires two factor security authentications to access. Once safely transferred to the SRD, all files will be deleted from Microsoft Teams and OneDrive.

All recordings and transcripts will be saved on the SRD using the study name, LA name and the date/time of the interview. Transcriptions will be anonymised. Audio recordings will be destroyed once transcriptions have been checked. Anonymous transcripts will be kept separately from identifying information, which will be retained for administration purposes until coding has been completed and then destroyed.

Due to the nature of the research topics, the research team is confident that the content of the interview data will fall within Level 2 or lower under the 'University data security classifications and guidelines', which is a requirement for data storage on the public cloud service when using Microsoft Teams.

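### Nothing in the protocol requires the rating of policy potential to be masked to arm and time point, so this secondary outcome can be biased towards the intervention

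*Protocol*

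**What the plan says.** Section 1.4.2 lists, first among the secondary outcomes, "Distribution of policies across a scale of potential to achieve system change (Potential of policies"). Section 3.3 analyses it in the same way as the primary outcome: "We will similarly assess changes in potential of policies to achieve system change". The protocol does not say what the scale is, who applies it, from which record, or when.

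On blinding, section 2.1 describes "A single-centre, unblinded, parallel-group, superiority randomised controlled trial with 1:1 allocation", and the synopsis also calls the trial unblinded. Section 3.2 says "Trial LAs will be unblinded (open label) and randomised using a computer-generated randomization list with a 1:1 ratio". No section provides for a masked assessor of any outcome.

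On roles, section 1.2 says that the intervention "will be delivered by the research team and comprise" the listed meetings and workshop. Section 2.5.1 says of the policy data: "Interviews will be conducted by a member of the research team with the LAKI" (the LA key informant).

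On records, the interview guide in Table 1 captures the LA name and the interview date. Section 2.5.1 keeps the recording and transcript only until a data capture form is complete. Section 4.1 says "All recordings and transcripts will be saved on the SRD using the study name, LA name and the date/time of the interview", and also that transcripts are anonymised and held apart from identifying information.

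**The concern.** Deciding how much potential a described policy has to change a system calls for judgement, and the protocol gives no mechanical rule that would replace it. Judgement ratings are open to expectation. Here the expectation runs one way: the team that helped to develop the workshop, and that delivers it, would be rating policies from the LAs that received it.

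A slight and unintended upgrade of 12-month policies from workshop LAs would look like a treatment effect. Randomisation balances the LAs, not the rater's expectations. Adjustment for baseline does not help either, because the shift would arise in one arm and only after baseline. The LAs cannot be blinded to a workshop, but a rater reading a written policy description can be.

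**Working it through.** **Step 1. Is unmasked rating permitted as the protocol stands?**

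| Question | Where | Answer |
|---|---|---|
| Is the outcome compared between arms? | 3.3 | Yes, from baseline and 12 months |
| Is there an objective scoring rule? | 1.4.2, 3.3 | None given |
| Is any assessor masked? | Synopsis, 2.1, 3.2 | No provision; the trial is unblinded |
| Who delivers the intervention? | 1.2 | The research team |
| Who collects the policy data? | 2.5.1 | A member of the research team |
| Which record is rated? | Not stated | Possibly the data capture form; the guide behind it records LA name and date |
| Is arm unknown at the baseline interview? | 2.5.1 | Yes, it precedes randomisation, but the time of rating is not fixed |

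Pre-randomisation collection protects the baseline interview. It does not protect the 12-month data, nor any rating done after allocation. Nothing in the protocol rules out a rater who knows both arm and time point.

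**Step 2. Check of the formula.** The protocol gives no figure for this outcome. Its power figures for the primary outcome (section 3.1) serve to check the calculation. For a two-sided 5% t-test (the 5% is assumed, as section 3.1 does not state it) with n = 30 per arm and 58 degrees of freedom, the noncentrality is (difference / SD) / √(2/n), with √(2/30) = 0.258.

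- SD 3: (2/3)/0.258 = 2.58, power 71.9% (protocol: 72%).
- SD 2: (2/2)/0.258 = 3.87, power 96.8% (protocol: 97%).

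Both reproduce.

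**Step 3. Illustration of a rating shift.** Assume no true effect, an LA-level mean score, and a shift of b SDs in the intervention arm at 12 months. The chance of a significant result is the power at noncentrality b/0.258.

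| Assumed shift b (LA-level SDs) | Noncentrality | False-positive rate |
|---|---|---|
| 0 | 0 | 5.0% |
| 0.1 | 0.39 | 6.7% |
| 0.2 | 0.77 | 11.9% |
| 0.3 | 1.16 | 20.8% |
| 0.5 | 1.94 | 47.8% |

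**Step 4. Effect of baseline adjustment.** Section 3.3 plans a baseline-adjusted regression. With an assumed baseline correlation of 0.5, the residual SD is √(1 − 0.25) = 0.866 of the unadjusted SD. A shift of 0.2 SD becomes 0.2/0.866 = 0.23 residual SDs, and shifts of 0.3 and 0.5 become 0.35 and 0.58. The false-positive rates become about 14%, 26% and 59%. Adjustment leaves the shift in place and reduces the noise around it.

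The values of b and the correlation are assumptions, and so is summarising the outcome as an LA mean.

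**The case against.** **The protocol is silent on rating, and that detail may belong elsewhere.** Scale levels, coding rules and double rating are often left to a statistical analysis plan or coding manual, and their absence here is no finding. Section 3.2 attaches the open-label statement to the LAs, so it does not exclude a masked rater. This stands in part. But who is masked is a matter of trial design, and section 2.1 describes the whole trial as unblinded without exception.

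**The scale might be rule-based.** If so, there would be less room for judgement. Nothing in the protocol says that it is, and sorting described policies by potential would normally still need some interpretation.

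**The file-naming rule.** A reader might infer that naming files by LA and date/time (section 4.1) by itself defeats masking. The documents do not support that. The same section anonymises transcripts and keeps them apart from identifying information, section 2.5.1 points to a data capture form, and no section says that ratings are made from the named files. A masked extract can be prepared whatever the source file is called. Equally, the anonymisation is a confidentiality measure and is not described as masking of arm or time point.

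**Importance.** A reader might also take this to be the only outcome that bears on the intervention's purpose. It is not. Section 1.1 refers to supporting LAs to implement policies that reduce dietary health inequalities, which the primary outcome counts. Understanding and collaboration are separate secondary outcomes.

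**Magnitude.** The illustration shows only that a sufficiently large bias yields false positives, which is true of any rated outcome. This stands: the figures are not an estimate of the bias in this trial.

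**Conclusion.** The point holds as a design weakness in one secondary outcome. The protocol permits policy potential to be rated with knowledge of arm and time point, by members of the team that delivers the workshops, and it makes no provision against this. Any resulting bias would most plausibly favour the intervention and would survive the planned adjustment.

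Its size is unknown. The false-positive rates of about 7% to 48% for shifts of 0.1 to 0.5 SD rest on assumed shifts, on an LA-level mean score and on an unadjusted t-test with 30 LAs per arm. The conclusion also assumes that placing a policy on the scale involves judgement, which the wording suggests but does not state. It makes no claim that raters will in fact be unmasked, only that the protocol allows it. The primary outcome is outside this point. The change is worth making because it is feasible and leaves sample size, intervention and interviews as they are.

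**What to change.** State in sections 2.1 and 3.3 that LAs and delivery staff are unblinded but that the rating of policy potential is masked to arm and time point, as follows.

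1. Take policy descriptions from the data capture form and give each a study ID.
2. Remove LA name, dates, arm and any reference to the workshop.
3. Pool descriptions from both arms and both time points, and rate them in random order after the last 12-month interview.
4. Use existing team members as raters. Someone who holds the ID key, and does not rate, assigns each LA's items to a rater who neither facilitated nor interviewed there. Each rater's set should mix arms and time points.

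Assigning items LA by LA means that no single rater need be uninvolved in all 60 LAs; the protocol does not show that such a person exists.

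Costs and limits: the redaction work covers up to 60 × 2 = 120 interviews, each possibly describing several policies. Ratings wait until follow-up ends. Masking will be imperfect where the content of a policy reveals the LA. The change gives no protection against reporting bias from unblinded key informants, which is a separate matter.

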2.5.2 Intervention workshop data collection

Subject to consent, we will carry out a short, Likert-style questionnaire at the start and end of the intervention workshop with all workshop participants to capture information on the majority of the secondary outcomes (**Table 2**). The questionnaire will be hosted within a purposely designed REDCap webform and links provided to workshop participants via email at the start and end of the day providing they have consented.

Table 2. Pre- and post-workshop questionnaire

| Statement (please circle your response for each statement) |
|--|
| 1. I have a good understanding of dietary inequalities in my local area 
 • Strongly agree • Agree • Neither agree nor disagree • Disagree • Strongly disagree |
| 2. My organization has a good understanding of dietary inequalities in our area 
 • Strongly agree • Agree • Neither agree nor disagree • Disagree • Strongly disagree |
| 3. I am committed to taking action to reduce dietary inequalities in my local area 
 • Strongly agree • Agree • Neither agree nor disagree • Disagree |

| |
|---|
| 
 • Strongly disagree |
| 
4. My organization is committed to taking action to reduce dietary inequalities in our area
 
 • Strongly agree • Agree • Neither agree nor disagree • Disagree • Strongly disagree |
| 
5. I am confident that I can contribute to reducing dietary inequalities in my area
 
 • Strongly agree • Agree • Neither agree nor disagree • Disagree • Strongly disagree |
| 
6. I am confident that my organization can contribute to reducing dietary inequalities in our area
 
 • Strongly agree • Agree • Neither agree nor disagree • Disagree • Strongly disagree |
| 
7. There will be meaningful collaboration between local partners to reduce dietary inequalities in our area over the next 12 months
 
 • Strongly agree • Agree • Neither agree nor disagree • Disagree • Strongly disagree |
| 
8. I am comfortable working with 'complex' or 'wicked' problems (these are problems that require intersectoral collaboration and not just more time and more money)
 
 • Strongly agree • Agree • Neither agree nor disagree • Disagree • Strongly disagree |

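### Confidence is defined as expecting additional solutions to be implemented within 12 months, but no questionnaire item asks this

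*Protocol*

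**What the plan says.** Section 1.4.2 of the protocol lists five secondary outcomes: the potential of policies to achieve system change, and four perceptions (Understanding, Commitment, Collaboration, Confidence). The last is defined as "Confidence that additional solutions to address DHI locally will be implemented in the next 12 months (Confidence", and the synopsis repeats that definition.

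Section 2.5.2 describes a Likert questionnaire given to workshop participants at the start and end of the workshop day, "to capture information on the majority of the secondary outcomes". Table 2 prints all eight items. Two concern confidence:

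- Item 5: "I am confident that I can contribute to reducing dietary inequalities in my area"
- Item 6: "I am confident that my organization can contribute to reducing dietary inequalities in our area"

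Section 3.3 plans to assess "Understanding, Commitment, Collaboration and Confidence in an RCT framework in LA key informants at baseline and 12 months", and to assess the same outcomes before and after the workshop in all workshop participants.

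**The concern.** The definition and the items are about different things. The definition concerns an event in the local area: new solutions being put into practice within a stated period. Items 5 and 6 concern capability: whether a person or an organisation is able to contribute. A respondent could strongly agree with both items and still expect nothing new to be implemented in the coming year. The reverse is also possible, if the respondent expects others to act.

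Research question 1 in section 1.3 asks for the impact of the intervention on the listed outcomes. If items 5 and 6 are reported under the Confidence label, readers will take a change in perceived capability for a change in expected implementation. Of the four perceptions, expected implementation lies closest to the primary outcome, which counts policies planned or implemented, so the mislabelling could mislead. Later analysis cannot repair it: a question that was not asked before a workshop cannot be recovered afterwards.

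**Working it through.** No arithmetic beyond counting applies. The check sets each perception outcome in section 1.4.2 against every item printed in Table 2, and then looks for another source in Table 1.

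**Table 2, by item**

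- Items 1 and 2: personal and organisational understanding. These correspond to Understanding.
- Items 3 and 4: personal and organisational commitment. These correspond to Commitment.
- Items 5 and 6: confidence that the respondent, or the organisation, can contribute. These are the only candidates for Confidence.
- Item 7: "There will be meaningful collaboration between local partners to reduce dietary inequalities in our area over the next 12 months". This is the only candidate for Collaboration.
- Item 8: comfort with complex problems. This matches none of the four definitions.

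The count is 2 + 2 + 2 + 1 + 1 = 8, so no item is left over.

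**Confidence, element by element**

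- Additional solutions: in the definition; in 0 of 8 items.
- Their implementation: in the definition; in 0 of 8 items.
- The next 12 months: in the definition; in neither item 5 nor item 6. In Table 2 this horizon appears only in item 7, which is about collaboration.

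**Another source.** The Table 1 guide asks about the local authority, the informant's role, food strategies and policies. Its substantive question begins "Can you tell me what policies have been put in place in the last 12 months or will be put in place". That elicits known or planned policies, not a rated belief, and the guide has no perception items.

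**Where the outcome is analysed.** Table 2 goes to workshop participants, who are recruited only in intervention authorities (section 2.3). It therefore supplies the uncontrolled start-to-end comparison. The randomised comparison in section 3.3 uses key informants in both arms, and the protocol names no instrument for measuring their perceptions.

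**Collaboration.** The definition is "Strength of local collaborations to address DHI (Collaboration". Item 7 asks whether meaningful collaboration will take place over the next 12 months. The wording differs, but the definition gives no tense, and an item about meaningful collaboration can be read as touching on strength.

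**The case against.** The questionnaire claims to cover only most of the secondary outcomes, so Confidence might be one that it leaves out. This does not stand. The natural exception is the potential of policies, which would draw on policy data, and section 3.3 expressly analyses Confidence before and after the workshop in the people who complete Table 2.

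Items 5 and 6 might be reasonable proxies. They are related to the outcome and worth keeping, but the protocol neither calls them proxies nor maps items to outcomes, and they omit every distinctive element of the definition.

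Three stronger readings are tempting but are not supported:

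- **Collaboration is equally unmeasured.** A reader might infer this from the forecast wording of item 7. But the definition does not say present strength, and existing partnerships could hardly change within one workshop day, so a forward-looking item is defensible there. This is a wording mismatch to tidy, not a second clear failure.
- **A mechanism analysis would rest on the wrong measure.** Section 2.8.1 says that the secondary outcomes include potential mechanisms, and section 2.8.2 names confidence among those theorised. But section 3.3 specifies no quantitative mechanism or mediation analysis, and the mechanisms objective belongs to the qualitative evaluation.
- **The randomised comparison will use items 5 and 6.** The protocol does not say so. Table 2 shows the mismatch for workshop participants; for key informants, the measure is simply not stated.

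**Conclusion.** The point holds for Confidence. One of five secondary outcomes (one of four perceptions) is defined in a way that 0 of 8 questionnaire items measure, and the other quantitative instrument shown does not fill the gap. If Table 2 is used as printed, the Confidence result in workshop participants will describe perceived ability to contribute. For key informants, no instrument is given at all. Collaboration is a minor matter of alignment.

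The primary outcome and its analysis are untouched, and the direction and size of any resulting error cannot be judged from the protocol. The conclusion assumes that Tables 1 and 2 are the complete quantitative instruments, as they are presented. It is worth correcting because the mismatch is plain in the text, the repair is small, and the pre-workshop answers cannot be collected later.

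**What to change.** Before recruitment, which section 2.7 anticipates from April 2026:

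1. Add one item to Table 2, on the same five-point scale: *I am confident that additional solutions to address dietary inequalities will be implemented in my local area in the next 12 months.* Name it in section 1.4.2 as the measure of Confidence, and keep items 5 and 6 as supporting items. Alternatively, leave Table 2 alone and redefine Confidence in section 1.4.2 and the synopsis as perceived ability to contribute.
2. State in section 2.5.1 that the chosen Confidence item is also put to key informants in both arms at baseline and 12 months. Changing Table 2 alone would leave the randomised comparison, including every control authority, without a stated measure.
3. As a minor edit, align the Collaboration definition and item 7, either by defining the outcome as expected collaboration or by wording the item as a rating of strength.

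The cost of the first option is one extra REDCap question per respondent at each administration, and a short protocol edit. For key informants, the item has to be added to the baseline and 12-month data collection. Redefining the outcome adds no question to Table 2, but gives up the outcome as now stated.
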